- Obstetric Quality of Recovery score using Obs-QoR-10 (Pervez Sultan et al. 2020; P Sultan et al. 2020)

How much have you been bothered by this problem in the past 24 hours?

1. Pain. 24 hours. None-worst imaginable 0-10. (P)
2. Nausea or vomiting. 24 hours. None-worst imaginable 0-10. (P)
3. Dizziness. 24 hours. None-worst imaginable 0-10. (P)
4. Shivering. 24 hours. None-worst imaginable 0-10. (P)
5. I have been comfortable. 24 hours. Not at all - all the time 0-10. (P)
6. I am able to mobilize independently. 24 hours. Not at all - all the time 0-10. (P)
7. I can hold my baby without assistance. 24 hours. Not at all - all the time 0-10. (P)
8. I can feed/nurse my baby without assistance. 24 hours. Not at all - all the time 0-10. (P)
9. I can look after my personal hygiene in the past 24 hours. 24 hours. Not at all - all the time 0-10. (P)
10. I feel in control in the past 24 hours. 24 hours. Not at all - all the time 0-10. (P)

- Global Health Score (Euroqol 2023) 24 hours. Worst-best imaginable health state 0-100 (for validation of Obs-QoR-10) (P)
- Response rates for questionnaires after 6,12,18,24,48 hours plus 7 and 30 days after the cesarean section.
- Response time for questionnaires after 6,12,18,24,48 hours plus 7 and 30 days after the cesarean section.

Neonatal outcomes

Primary outcome

- Need for neonatal admission within 24 hours (yes/no). (J)

Secondary outcomes

- Infants in need of respiratory support within 48 hours (continuous positive airway pressure treatment, positive pressure ventilation, HNF (nasal high flow), intubation or oxygen therapy). Yes/No and time (J)
- Proportion with established breastfeeding at 30 days following delivery, if intended. (P)

Exploratory outcomes

- Apgar score at 5 minutes. (J)
- Apgar score at 10 minutes. (J)
- Proportion of infants with Apgar <7 at 5 minutes. (J)
- Readmission within 24 hours after discharge. Yes/No.
- Readmission within 7 days after discharge. Yes/No.

Development and validation of questions:

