- Nerve blockade within the first 24 hours after the cesarean section: Yes/No; Time; Block type, dose, medication, reason.
- Placement of an epidural within the first 24 hours after the cesarean section: Yes/No; Time, reason

- Opioid consumption within 0-24 hours, mg oral morphine equivalents
- Opioid consumption within 25-48 hours, mg oral morphine equivalents
- Administration of dexamethasone within the first 24 hours after cesarean section: Yes/No. Dose.
- Administration of antihistamine as itch relief within the first 24 hours: Yes/No
- Administration of naloxone as itch relief within the first 24 hours: Yes/No

Maternal hospitalization

- Duration of total hospital lengths of stay after cesarean section (number of days)
- Maternal readmission or unplanned outpatient consultation within 7 days. Yes/No
- Occurrence of clinically significant maternal respiratory depression within 24 hours, defined as the need for airway intervention; oxygen therapy >3 L/min; administration of an opioid antagonist to counteract depressed respiration; or an intervention beyond verbal stimulus to rouse the patient from sedation. Yes/No
- Ogilvie's syndrome/ileus, that requires surgery or neostigmine within the first 7 days after cesarean section: Yes/No

Infant

- Apgar score at 5 minutes
- Apgar score at 10 minutes
- Neonatal hospitalization within 24 hours: Yes/No
- Neonatal readmission within 24 hours: Yes/No
- Neonatal readmission within 7 days: Yes/No
- Neonatal need for respiratory support within 48 hours (CPAP, PPV, HNF, intubation, or oxygen supplementation): Yes/No; Time of initiation; Duration (hours < 24 or number of days > 1)

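### Do the infant readmission fields, which omit the discharge anchor, leave the 7-day outcome open to different coding by site?

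*Protocol*

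**What the plan says.** Under Neonatal outcomes, Exploratory outcomes, the protocol lists "Readmission within 24 hours after discharge. Yes/No" and "Readmission within 7 days after discharge. Yes/No". Both windows start at discharge.

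Under Data to be collected from the patient's medical record, the Infant items include "Neonatal hospitalization within 24 hours: Yes/No", then "Neonatal readmission within 24 hours: Yes/No" and "Neonatal readmission within 7 days: Yes/No". Neither readmission item repeats the anchor, and no infant discharge or readmission date is listed. The only stay variable, "Duration of total hospital lengths of stay after cesarean section (number of days)", is listed under Maternal hospitalization.

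The Outcomes section sets the time of spinal anesthesia (t0) as the general origin for time intervals. Appendix 3 is named as the data extraction sheet for the record review, but its content is not shown.

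**The concern.** The definition and the field label differ by the words that fix the window. The surrounding items could suggest another origin. The infant hospitalization item directly above has no discharge anchor. The ileus item runs explicitly from the operation ("requires surgery or neostigmine within the first 7 days after cesarean section: Yes/No"). The maternal item, "Maternal readmission or unplanned outpatient consultation within 7 days. Yes/No", is not tied to discharge either. The only general origin given anywhere is t0.

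Each hospital has its own data manager and at least 9 centers take part, so one site might count from birth and another from discharge. The error would run one way: a readmission within 7 days of birth is always within 7 days of discharge, but not the reverse. Counting from birth can therefore only lose events, and misreadings would not cancel in the pooled figure. With Yes/No answers and no dates, the listed data could not show which window was used. The Objective section says that outcome frequencies will inform a later randomized trial, so an understated infant readmission frequency could be carried forward.

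**Working it through.** The plan gives no figure to reproduce: the sample is one of convenience and the analysis is descriptive. The check is a comparison of texts, plus a bound on the possible loss.

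**1. Is there a second definition?**

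| Item | Outcome section | Record list |
|---|---|---|
| Infant readmission, 24 hours | from discharge | no origin stated |
| Infant readmission, 7 days | from discharge | no origin stated |
| Opioid consumption, first 24 hours | from the cesarean section | no origin stated |
| Maternal readmission or visit, 7 days | no discharge anchor | no discharge anchor |
| Ileus, 7 days | not an outcome | from the cesarean section |

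The record list never gives infant readmission a different origin. It also drops the origin for opioid consumption, where the outcome section supplies one, so shortening is how the list is written. The ileus item has no outcome definition to lean on and must carry its own anchor. The maternal item matches its own definition. The infant hospitalization item describes a different event, the admission that forms the primary neonatal outcome. None of these redefines infant readmission.

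**2. Does t0 override the anchor?** The t0 convention is introduced for the outcome measures. Within that section, the specific reference to discharge takes precedence over the general default.

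**3. What would be lost if a site did count from birth?** Let L be the infant's stay in days. The documents give no value, so L = 1 to 4 is an assumption. Post-discharge days covered = 7 − L, and share of the window lost = L/7.

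| L (days) | Days covered | Lost at that site | Pooled loss if half the infants are so coded |
|---|---|---|---|
| 1 | 6 | 1/7 = 14% | 7% |
| 2 | 5 | 2/7 = 29% | 14% |
| 3 | 4 | 3/7 = 43% | 21% |
| 4 | 3 | 4/7 = 57% | 29% |

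Reading lost days as lost events also assumes a constant readmission rate over the window. The share of one half is an assumption too. These are relative losses on a frequency the documents do not give, and they are zero if every site follows the definition.

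**4. Is the from-birth reading plausible?** Apply it to the 24-hour field. With L of 1 day or more, the post-discharge time inside a 24-hour window from birth is at most 24 − 24 × 1 = 0 hours, so the field could never be answered yes. The 24-hour and 7-day items are adjacent and worded alike. A data manager who sees that the first must run from discharge has good reason to read the second the same way.

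**5. Can the outcome be derived?** It is defined as Yes/No and collected as Yes/No. Coded to its definition, the field is the outcome. Dates would allow verification but are not needed for derivation.

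**6. Is the window observable?** With L up to 4, it closes at day 4 + 7 = 11 at the latest. The same record review must already look back over 30 days for reoperation.

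**The case for a change.** The strongest counter-argument is that this cannot be left to the analysis stage: if an anchor or date is not recorded, no analysis plan can restore it. Many people at separate hospitals extract the data, the error would be one-sided, and two reworded labels would cost almost nothing.

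Part of this stands. The labels are shorter than the definition, and from the listed items alone nobody could audit which window a site used. Maternal length of stay is only a rough proxy for infant discharge, and without a readmission date it would not permit recoding.

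What does not stand is the step from there to two outcomes that cannot be derived as defined. That requires a data manager to set aside the protocol's definition in favour of an origin the list does not state for this event, and one that would empty the neighbouring field. It also requires Appendix 3 to be silent, which cannot be known because the sheet is not shown. The link to the later trial is a general statement about outcome frequencies and does not mention infant readmission. The protocol gives high priority to opioid side effects, and its primary neonatal outcome is admission within 24 hours, which this point does not touch.

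**Conclusion.** No change to the plan is called for. The discrepancy is real but editorial: a field label omits words that the outcome definition supplies. Coding the field to the definition, as a site working from the protocol would, gives a sound descriptive frequency.

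If some sites did misread the label, the effect would be a one-sided understatement of the 7-day infant readmission frequency. The 14% to 57% per-site figures bound it only under an assumed stay of 1 to 4 days and a constant readmission rate; the pooled 7% to 29% also needs half the infants to be miscoded. None of these inputs comes from the documents. The primary and secondary outcomes, maternal and neonatal, are unaffected.

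The conclusion rests on sites reading the record list together with the outcome definitions, and on Appendix 3 not stating a contrary origin. Repeating the anchor in the two labels would be harmless tidying, and recording infant discharge and readmission dates would be an optional check. Neither is needed for the outcomes to be reported as defined.

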That dosage is significantly higher than recently described in a Danish uni-center quality study of 100 patients ([name] 2023). Among these patients, 85 received the standard postoperative pain management for cesarean section, which aligns with the pain treatment protocols employed in most hospitals across the country: A fixed dose of paracetamol and NSAID, supplemented with oral morphine; nerve blocks or intrathecal morphine are not given routinely. The median 24-hour oral morphine equivalent dose given to the patients by request to the nurses was 30 mg (IQR: 20-50). The relatively lower opioid dose may suggest an existing underestimation and suboptimal treatment of the patients' pain. At 6, 12, 18 and 24 hours after the cesarean section the reported average NRS (0-10) pain scores during movement were 7,

6, 6, and 5 respectively, corresponding to moderate or severe pain, and further supports the possibility of underestimation and undertreatment of post-cesarean pain.

In a Danish multicenter survey conducted in 2020 to 2021 (Lindelof 2022), 861 cesarean section patients were asked 24-48 hours after surgery how much they agreed on having “experienced severe pain after the cesarean section” In this assessment, 45% scored ≥ 8 (NRS 0-10).

Overall, there is strong indications that currently a substantial number of women in Denmark experience severe pain in the first days after their cesarean section. To address this, we have established an obstetric-anesthesiologic research cluster as part of the national perioperative research network, CEPRA (Nørskov et al. 2023) with an aim to optimize pain treatment for the approximately 12,700 Danish patients who undergo cesarean section every year.

Objective

This study aims to map postoperative pain in Danish patients undergoing elective cesarean section. Specifically postoperative pain levels, impact on physical function, side effects from pain medication, and treatment approaches in the postoperative period.

Furthermore, we aim to test the feasibility of repeated SMS-based questionnaires sent to the patients in the postoperative period. Based on response rates and frequency of outcomes, data from this observational study will also be used to inform a randomized controlled multicenter trial aiming to test better postoperative pain interventions for cesarean section patients.

Method

Study design

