Prospective Danish multicenter cohort study based on patient-reported outcomes (SMS-based questionnaires) and clinical data from electronic health records.

Inclusion criteria

Patients who undergo planned cesarean section under spinal anesthesia.

Patients who speak and read Danish and can provide informed consent to participate.

Patients who have a smartphone that can receive an SMS with a link to a questionnaire that can be accessed on an online website on the phone.

Exclusion criteria

Age < 18 years

Number of participants

Minimum 400 patients, included from minimum 9 centers representing all 5 regions in Denmark.

Outcomes

Outcomes have been selected to align with the outcomes in a subsequent randomized controlled multicenter trial, where we will investigate whether the addition of intrathecal morphine provides better postoperative pain control. Therefore, opioid side effects are given high priority in the outcome measures.

The following abbreviations are used in the section outcome measures:

Time intervals are specified as the time difference from the administration of the spinal anesthesia (t0), and outcomes are assessed either through patient questionnaires (P) or by reviewing medical records (J).

Outcome measures

Maternal outcomes

Primary outcomes

- Level of pain during the activity from lying to a seated position, after 24 hours. NRS 0-10 (P)
- Morphine associated adverse events within 24 hours after CS, assessed as a binary outcome including nausea, vomiting, dizziness, itching, or urine-retention (P). Vomiting and urine-retention, will be reported as yes/no. Nausea, dizziness and itching will be assessed as “none”, “little”, “moderate”, or “severe”, with patients reporting “moderate” or “severe” categorised as having a positive outcome.

Secondary outcomes

- Opioid consumption within the first 24 hours after caesarean section (oral morphine equivalents, mg) (J)
- Insufficient spinal anesthesia related adverse events during the caesarean section, as binary composite outcome of the proportion of patients in need of conversion to general anesthesia, intraoperative opioids, sevoflurane, or nitrous oxide for intraoperative pain, or repeated neuraxial procedure (spinal or epidural placement following failed spinal). (J)
- Level of pain during the activity from a lying to a seated position, after 6, 12, 18 hours. NRS 0-10 (P)
- The ability to mobilize independently at 24 hours after surgery. Yes/No (P)

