- The ability to nurse infant independently at 24 hours after surgery. Yes/No (P)

Exploratory outcomes

- Level of pain at rest 6, 12, 18, 24, 48 hours, 7 days, and 30 days after surgery. NRS 0-10 (P)
- Use of analgesic medication (Paracetamol (PCM), Non-Steroidal Anti-Inflammatory Drug (NSAID) and opioid) 6, 12, 18, 24, 48 hours, 7 days, and 30 days postoperatively. Yes/No. (P)
- Level of pain during the activity from a lying to a seated position after 48 hours, 7 days and 30 days. NRS 0-10 (P)
- Localization of pain: Abdomen, shoulder, head, back, other. 6, 12, 18, 24, 48 hours. (P)

- Need for unplanned "rescue" ultrasound-guided truncal nerve block or epidural within 24 hours. Yes/No (J)
- Maternal satisfaction with pain-treatment during the first 24 hours. Assessed after 24 hours. Likert scale of 0-4. Very dissatisfied, dissatisfied, neither satisfied nor dissatisfied, satisfied, very satisfied. (P)
- Pain related self-efficacy and self-empowerment after surgery: The feeling of being in control during the first 24 hours, assessed after 24 hours, Likert scale (0-4). (P)
- Composite outcome of rare maternal adverse events (J):
 - Clinically significant maternal respiratory depression within 24 hours defined as the need for airway intervention; oxygen therapy >3 L/min; administration of an opioid antagonist to counteract depressed respiration; or an intervention beyond verbal stimulus to rouse the patient from sedation reported the first 24h after surgery *or*
 - Maternal hospital readmission within 7 days, *or*
 - Maternal re-attendance or unplanned out-patient visit within 7 days.
- The ability to handle own personal hygiene 24 hours after surgery. Yes/No (P)
- Itching after 6, 12, 18, 48 hours, 4-point scale: None, mild, moderate, severe (P)
- Dizziness after 6, 12, 18, 48 hours, 7 days, and 30 days, 4-point scale: None, mild, moderate, severe (P)
- Nausea after 6, 12, 18, 48 hours, 7 days, and 30 days, 4-point scale: None, mild, moderate, severe (P)
- The impact of pain on how often the patient has gotten out of bed in the last 6 hours. 6, 12, 18, 24, 48 hours. 4-point scale: None, a little, moderate, a lot (P).
- The impact of pain on how much the patient has breastfed or bottle-fed the infant in the last 6 hours? 6, 12, 18, 24, 48 hours. 4-point scale: None, a little, moderate, a lot (P).
- The impact of pain on the ability to resume regular daily activities. 7 and 30 days. 4-point scale: None, a little, moderate, a lot (P)

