The questions were developed with inspiration from international consensus regarding obstetric recovery, including the incorporation of the Obs-QoR-10 score (Pervez Sultan et al. 2020; P Sultan et al. 2020) and the use of NRS scores for pain assessment (Eisenach et al. 2008; Hansen et al. 2019). Additionally, we have drawn on experience and knowledge gained from the pilot study by [name] et al. ([name] 2023) preceding this national study, which involved the participation of 100 patients. Patients, maternity staff, anesthetists, and obstetricians was consulted to determine the key areas of focus during the first postoperative days after a cesarean section. The questions were developed and validated by using standardized methods for designing and conducting surveys (Eysenbach 2004; Burns et al. 2008). Subsequently, the questionnaires were created in the database: Research Electronic Datacapture (REDCap) (“RedCap” n.d.)

Data collection

All data is entered directly into the closed and secure system, REDCap (Harris et al. 2009), which is approved by all the regions in Denmark. Questionnaires are sent to the patient after 6, 12, 18, 24, and 48 hours, as well as 7 and 30 days after spinal anesthesia for cesarean section (t0). The questionnaires are delivered to

the patient's smartphone as an SMS with a link to a questionnaire in REDCap. Data from journal entries are also entered into REDCap. At all hospitals, there is a data manager who has access to REDCap and can retrieve data for the patients included in the project. The primary investigator holds the overall responsibility.

Ethics and approvals

This study complies with the Helsinki declaration. The protocol will be made available on the website clinicaltrials.gov prior to inclusion of patients. Participation is completely voluntary, and consent can be withdrawn at all times.

Data Protection Authority

Approval for data collection, handling and storage has been granted by the data protection authority for the Capital Region (Region Hovedstaden) with case number P-2023-90. This includes approved data agreements between the Danish Regions, with a designated data manager from each participating hospital. (See Appendix 1)

Research Ethics Committee

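### Does a 6-hourly SMS schedule with no stated reply window leave the first-day scores and response rates poorly defined?

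*Protocol*

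**What the plan says.** The Outcomes section sets the clock: "Time intervals are specified as the time difference from the administration of the spinal anesthesia (t0"), so each patient has her own time zero. Data collection then fixes the sending times: "Questionnaires are sent to the patient after 6, 12, 18, 24, and 48 hours, as well as 7 and 30 days after spinal anesthesia".

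The maternal secondary outcomes include "Level of pain during the activity from a lying to a seated position, after 6, 12, 18 hours"; the 24 h movement score is a primary outcome. Among the maternal exploratory outcomes, two impact items look back six hours, for example "The impact of pain on how often the patient has gotten out of bed in the last 6 hours", and Obs-QoR-10 asks "How much have you been bothered by this problem in the past 24 hours". The same list contains "Response rates for questionnaires after 6,12,18,24,48 hours plus 7 and 30 days after the cesarean section" and "Response time for questionnaires after 6,12,18,24,48 hours plus 7 and 30 days after the cesarean section".

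The Objective section makes feasibility of the SMS questionnaires an aim and adds: "Based on response rates and frequency of outcomes, data from this observational study will also be used to inform a randomized controlled multicenter trial".

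The protocol text gives no link expiry, no reminder rule and no limit on how late a reply may be. Appendix 4, the overview of the questions as set up in REDCap, is listed by title only.

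**The concern.** Messages six hours apart cannot all avoid the night. If a sleeping patient answers the 18 h message in the morning, her score carries the 18 h label but describes a later time, possibly close to her 24 h answer. Items that look back six hours drift with the reply, because as worded they are not tied to the spinal.

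The 12 h and 18 h movement scores are secondary outcomes, so blurred time points would matter. The response rate is also meant to guide a randomized trial, and without a time limit it can mean either any reply or a timely one. Link expiry and item wording have to be settled before the first message goes out, so it seems natural to ask for them in the protocol.

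**Working it through.** The protocol gives no power or sample-size calculation to reproduce; the sample is one of convenience. The check covers the clock, the look-back periods and the possible size of the effect.

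**1. Night messages.** For a spinal at clock time t0, count the sends at t0 + 6, 12, 18 and 24 h (modulo 24) that fall in 00:00–05:59. For all 1,440 possible start minutes the count is exactly 1.

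| Spinal given | Night message |
|---|---|
| 06:00–12:00 | 18 h |
| 12:00–18:00 | 12 h |
| 18:00–24:00 | 6 h |
| 00:00–06:00 | 24 h |

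The protocol gives no surgery hours. If starts are spread evenly over 08:00–15:00 (assumption), 4/7 = 57% of patients get the 18 h message at night and 3/7 = 43% the 12 h message. The 24 h message arrives at the clock time of the spinal, so by day.

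**2. Look-back periods.** A six-hour item sent at 18 h and answered d hours late covers 12 + d to 18 + d. The share beyond 18 h is d/6:
- d = 1: 1/6 = 17%
- d = 3: 3/6 = 50%
- d = 6: 6/6 = 100%

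For Obs-QoR-10 the share still inside the intended day is (24 − d)/24; at d = 6 it is 18/24 = 75%.

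These items are exploratory. The primary adverse-event composite and the separate satisfaction and control items are tied to the first 24 hours and do not drift in this way.

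**3. Effect on pain scores.** The Background gives pilot mean movement scores of 7, 6, 6 and 5 at 6, 12, 18 and 24 h. If a fraction f of 18 h replies is really given at 24 h, the 18 h mean reads (1 − f) × 6 + f × 5 = 6 − f:
- f = 0.10: 5.9
- f = 0.25: 5.75
- f = 0.50: 5.5

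These fractions are assumptions. If only night replies are late, f = 0.50 requires 0.50/(4/7) = 87.5% of them to be a full six hours late, which is extreme. For 12 h replies given at 18 h the shift is 6 − 6 = 0. No pilot score exists after 24 h, so no shift can be computed for the primary score. Data Processing and statistics reports medians unless the data are normal, and a median may not move at all.

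**4. Effect on the response rate.** If 80% ever answer (assumption), the timely rate is 0.80 × (1 − f):
- f = 0.10: 72%
- f = 0.25: 60%
- f = 0.50: 40%

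**5. Can both rates be obtained?** For any limit w, the timely rate is the number of replies with response time up to w, divided by the number of messages sent. Response time is collected for every questionnaire, so the any-time rate, the timely rate and the actual hours since t0 are all available. w need not be fixed before data collection for them to be computed.

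**6. Would a fixed limit help?** Half the spacing gives 3 h. For a spinal at 06:00–10:00 the 18 h message goes out at 00:00–04:00, and a 3 h limit closes at 03:00–07:00. Many ordinary morning replies would then no longer count at 18 h.

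**The case for a change.** The strongest case for a change is that some things cannot be repaired afterwards. A pain score can be moved to its true time, but a six-hour look-back item answered at 24 h cannot be turned back into an answer about 12–18 h. If links do not expire, nothing in the protocol text prevents a patient from answering the 18 h and 24 h questionnaires together, which gives two records of one moment. Feasibility is a stated aim, and the gap between 80% and 72–40% in step 4 could affect the design of the randomized trial. A few lines of text would settle it.

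Part of this stands. The protocol does not say which response rate is meant, and the six-hour items can drift. But the items that cannot be repaired are exploratory, and their exact wording and possibly their settings belong to Appendix 4, which is not reproduced. Two questionnaires answered together would show in the response times. Testing whether patients answer on such a schedule is one purpose of the study, so late night replies are a result to report rather than a fault in the design.

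**Conclusion.** No change to the protocol follows. The night message is certain for every patient, but it comes with any 6-hourly assessment over a full day, and setting a reply window would leave the schedule as it is. What is missing is an acceptance window and a definition of response rate. Such detail is commonly left to the SAP, and a sensible analyst can supply it from the response times already collected, reporting any-time and timely rates side by side. A short reply limit is a debatable trade-off, because it would drop many of the night replies.

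The effect on scores is small and rests on assumed late shares: 0.1 to 0.5 points on the 18 h mean, none at 12 h, possibly none in a median, and none computable for the 24 h primary score. The response rate could differ more, 80% against 72–40% under the same assumptions, but both figures can be recovered from the data. The night-time drop in replies cannot be estimated from the protocol.

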Pain after Cesarean section- A Danish multicenter cohort study.

Document date: 11.8.23

NCT ID: Not yet assigned

Background

Worldwide, more than 20 million children are born by cesarean section each year (World Health Organization 2021), making it one of the most commonly performed surgical procedures. Postoperative pain is typically moderate to severe in intensity (Sun and Pan 2019) and inadequate pain relief significantly affects the new mother's ability to mobilize and care for herself and her baby (Ciechanowicz et al. 2019). Pain may also impact recovery and negatively affect the early bonding between mother and child, as well as the establishment of breastfeeding (Roofthoof et al. 2021). Furthermore, there might be a correlation between inadequately treated acute pain and the development of chronic pain after cesarean section (Nikolajsen et al. 2004; Yimer and Woldie 2019). All these factors emphasize the necessity of effective pain management following cesarean section.

Only a few studies describe pain following cesarean section in a Danish population. Nikolajsen et al. (Nikolajsen et al. 2004) investigated the prevalence of chronic pain among 220 patients interviewed one year after cesarean section. A total of 46.8% recall to have experienced severe pain in the period shortly after the cesarean section. In a Danish randomized placebo-controlled trial involving 72 patients (Hansen et al. 2019) reported pain scores in patients allocated to either a Transmuscular Quadratus Lumborum block (TQL) or placebo TQL following a cesarean section. Both groups had access to intravenous morphine via patient-controlled analgesia. The patients scored their pain on a numeric rating scale (NRS), ranging from 0 to 10, where 0 is no pain and 10 is the most severe pain imaginable. After 6 hours, the TQL block group had an NRS (0-10) of 4 during movement, while the placebo group had an NRS of 5. At 12, 18 and 24 hours, both groups had similar NRS scores of 5, 4, and 3, respectively. The average 24-hour oral morphine equivalent consumption was 65 mg for the TQL block group, compared to 94 mg for the group given placebo.

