The Research Ethics Committee (VEK) and the regional research ethics committee for the Capital Region of Denmark (Region Hovedstaden) have been presented with the project description and protocol and have waived the need approval due to Danish legislation. Case number F-23004686. (See Appendix 1)

Informed consent

Verbal informed consent is obtained during the inclusion process with each patient. The patient must consent to receive questionnaires on the mobile phone and to the data manager accessing the medical records related to the cesarean section for the patient and the baby. The patient is informed that participation is voluntary and that their data will be securely stored. Written description of the consent is electronically sent to the patient, including a description of how to withdraw consent. This is approved by the data protection authority for the Capital Region of Denmark (Region Hovedstaden) with case number P-2023-90

Data Processing and statistics

All data will be handled in the secure REDCap database. Descriptive statistics will be used to analyze data. Continuous data will be summarized as median (interquartile range) or mean if the data is normally distributed. We plan to do a subgroup analysis on the groups where intrathecal morphine or TQL block has been administered. And categorical data as frequency (percentage). We will try to minimize missing data as much as possible, by sending questionnaires directly to the participants mobile phones. Number of missing data will be accounted for when describing data. Sample size is determined by convenience. The study is designed to be as large as possible, as all hospitals in Denmark, handling elective cesarean sections, will be invited to participate. Larger sites (>300 elective CS per year) commits to include 50 patients, medium scale sites (200-300 elective CS per year) commit to include 40 patients, and smaller sites (<200 elective CS per year) commits to include 30 patients.

Collaboration Agreement

A collaboration agreement has been established between project leaders and site coordinators, outlining mutual obligations and rules for data usage.

Inclusion Period

01.09.2023-31.12.2024, 1-6 months depending on the rate of inclusion at different sites.

Participating Departments

Maternity units from all 5 Danish regions. The following hospitals have agreed to participate:

Capital Region of Denmark (Region Hovedstaden): Hilleroed, Herlev, Hvidovre, Rigshospitalet

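### Does the rule for summarising continuous data leave the later trial without the mean and SD of the pain score?

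*Protocol*

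**What the plan says.** In the Protocol, the section Data Processing and statistics makes the whole analysis descriptive. For continuous variables it says "Continuous data will be summarized as median (interquartile range) or mean if the data is normally distributed". For the rest it says "And categorical data as frequency (percentage"). It names no normality test or other criterion, and no measure of spread beside the mean.

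Under Outcome measures, the first primary maternal outcome is "Level of pain during the activity from lying to a seated position, after 24 hours. NRS 0-10 (P"). The second, morphine-associated adverse events, is binary. The Outcomes section adds: "Outcomes have been selected to align with the outcomes in a subsequent randomized controlled multicenter trial".

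The Objective section says how the cohort will serve that trial: "Based on response rates and frequency of outcomes, data from this observational study will also be used to inform a randomized controlled multicenter trial".

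The Background reports doses from two earlier Danish studies. For the randomised block trial: "The average 24-hour oral morphine equivalent consumption was 65 mg for the TQL block group", against 94 mg with placebo. For the single-centre quality study: "The median 24-hour oral morphine equivalent dose given to the patients by request to the nurses was 30 mg (IQR: 20-50").

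**The concern.** An 11-point whole-number score cannot be exactly normal. With about 400 patients a sensitive test will detect this, so the pain score could be reported only as a whole-number median with an IQR. A less sensitive judgement, made separately at each time point, could give a mean at one hour and a median at another and so break up the 6-12-18-24 hour course. Neither branch promises an SD.

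If the later trial were powered on the 24-hour score, it would need an SD, and one inferred from a rounded IQR is coarse. The Background seems to show the cost of mixing statistics: it sets mean doses against a median dose and reads the gap as possible undertreatment.

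**Working it through.** The Protocol gives no power-based figure to reproduce, because its sample size (at least 400) is set by convenience. The means, SDs, 1-point difference, 90% power and lognormal shape below are assumptions. The means of 5 to 7 span the pilot averages in the Background.

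**1. Does the rule force a median?** Scores were simulated as normal values, rounded and clipped to 0-10, with 1000 runs per setting and tests at the 5% level. Share of runs rejecting normality at n = 400:

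| Mean, SD | Shapiro-Wilk | D'Agostino-Pearson |
|---|---|---|
| 5, 1.5 | 100% | 4% |
| 5, 2.0 | 100% | 4% |
| 6, 2.0 | 100% | 16% |
| 7, 2.0 | 100% | 90% |
| 5, 2.5 | 100% | 76% |

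The outcome depends on a test that the Protocol does not name, and a visual check could also lead to the mean. At n = 30, a size the planned intrathecal morphine or block subgroups might have, Shapiro-Wilk rejects in only 10-55% of runs, and 10-20% of medians are half-points. At n = 400, medians are whole numbers in practically every run.

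**2. What does a whole-number median hide?** With SD 2.0 or 2.5, underlying means from about 4.6 to 5.5 all give a median of 5. This coarseness is real. It is a property of the summary, and the IQR is reported with it.

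**3. Would the SD have to be guessed?** For a difference of 1 point, two-sided alpha 0.05 and 90% power, n per arm = 2 × SD² × (1.96 + 1.2816)².

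- SD 2.5: 2 × 6.25 × 10.508 = 131.4, so 132.
- SD 3.0: 2 × 9 × 10.508 = 189.1, so 190, which is 44% more.

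That spread matters only to someone who has the published IQR and nothing else. The Outcomes section says that the same group will run the later trial, and the Data collection section places every response in REDCap, so the group can compute the SD from the records. With 400 responses and roughly normal scores, its relative standard error is about 1/√(2 × 399) = 3.5%. An SD of 2.5 would then be known to within about 1.96 × 3.5% = 7%, or roughly 2.3 to 2.7.

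**4. What is the trial to be planned on?** The Objective names response rates and the frequency of outcomes. Both are proportions, which the categorical rule reports. Nowhere does the Protocol say that the trial will be powered on a mean pain score.

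**5. Are the earlier pain data averages?** The Background has three recent Danish sources with 0-10 scores. The single-centre study's scores are called averages (7, 6, 6, 5). The block trial's scores carry no stated summary type. The national survey gives a proportion, 45% scoring 8 or more. Only one of the three calls for a mean.

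**6. The dose comparison.** For a lognormal with quartiles 20 and 50, sigma = ln(50/20) / (2 × 0.6745) = 0.679.

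- Mean from the median: 30 × exp(0.679²/2) = 37.8 mg.
- Mean from the log-midpoint of the quartiles: √(20 × 50) × 1.259 = 39.8 mg.

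Using the mean removes 8-10 mg of the gaps of 35 mg (65 − 30) and 64 mg (94 − 30). About 25-27 mg and 54-56 mg remain.

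**The case for a change.** The strongest case for a change is that this sentence stands in the Protocol itself and governs the whole analysis. It offers a mean without a spread and lets an undefined, data-dependent condition choose the statistic. Applied mechanically, it could split one outcome. With SD 2.0 at both hours, D'Agostino-Pearson at n = 400 rejects in about 90% of runs at a mean of 7 (the pilot's 6-hour average) but in about 4% at a mean of 5 (its 24-hour average). That would usually give a median at 6 hours and a mean at 24 hours. Outside readers and meta-analysts, who lack the patient-level data, would be the ones to lose.

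It stands that the sentence names neither an SD nor a criterion, and that printing mean (SD) beside median (IQR) would help outside readers. It does not follow that the plan is wrong. Nothing requires a formal test at each time point, and an analyst would give an SD with a mean and use one summary across a repeated outcome as a matter of course. Such details are commonly left to a statistical analysis plan, which may exist but is not shown.

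**Conclusion.** The concern does not hold. Median (IQR), or mean where the data are normal, is a conventional and valid rule for a descriptive cohort, and following it gives sound results.

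The supposed harms do not arise. The median branch is certain only under one test that the Protocol does not name. The later trial is to rest on response rates and outcome frequencies. The group planning it has the records from which to compute an SD. The Background's dose comparison does not come from this rule, and a gap of at least 25 mg survives the 8-10 mg correction.

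Asking for mean (SD), median (IQR) and the full distribution together is a reasonable reporting preference, but it changes no conclusion of the study. This judgement rests on the trial being planned as the Objective and Outcomes sections describe. The simulated rates and the dose correction rest on the assumed score distributions and the lognormal shape.
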